## **6.0 Visit Schedule and Assessments:**

### **Pretreatment evaluation**

Pretreatment evaluation will include a physical examination, height and weight and recording of concurrent medications (within 7 days of registration).

**Chemistry:** Clinical laboratory evaluation will include serum chemistry. This will include sodium, potassium, calcium, magnesium, phosphorus, BUN, creatinine, glucose, albumin, total protein, alkaline phosphatase, total bilirubin, ALT, uric acid, and TSH. Beta-2-microglobulin (within 7 days of registration).

**Hematology:** Complete CBC and differential and peripheral blood lymphocyte subset and immunoglobulin levels (within 7 days of registration).

Bone marrow aspiration and biopsy within one month from registration. Bone marrow will be evaluated by flow cytometry for clonality and for IgVH mutation studies (unless known) ZAP-70 expression (unless known), cytogenetic and genomic abnormalities (unless known).

HIV, Hepatitis B and C screening (if not performed within 3 months from registration).

### **Evaluation During Study**

Monitoring will consist of biweekly (every other week  $\pm 3$  days) blood counts and SMA12 during treatment, then every 3 months ( $\pm 2$  weeks) during follow-up until alternative treatment for CLL or death, whichever occurs first. For patients who are HBsAg-, HBcAb+, HBsAb+/-, and HBV DNA- on enrollment and proceeded with treatment, HBV DNA PCR testing will be done every 2 months while on treatment and maintenance, then every 3 months during follow-up for 6 months.

A physician will see patients at least monthly ( $\pm 5$  days) during treatment, then every 6 months ( $\pm 2$  weeks) during follow-up. All patients will be followed for survival.

CD4+, CD8+ and peripheral blood lymphocyte subset, beta-2-microglobulin will be analyzed after month 6 and every six months thereafter. Bone marrow biopsy and aspiration will be performed as clinically indicated after month 6 and every six months thereafter.

## **7.0 Criteria for Response**

The 2008 NCI Working Group criteria for response will be used. Response will be assessed after month 3, month 6 and every 6 months thereafter.

## 8.0 Evaluation of Toxicity

Toxicity will be scored using CTC Version 4.0 for toxicity and adverse event reporting according to the M.D. Anderson guidelines. Hematologic toxicity will be assessed, graded, and summarized according to the 2008 IWCLL Guidelines (See Table 3). Adverse events will be documented in the medical record and entered into the case report form according to the Leukemia-Specific Adverse Event Recording and Reporting Guidelines (Appendix D). PDMS/CORe will be used as the electronic case report form for this protocol. The Investigator or physician designee is responsible for verifying and providing source documentation for all adverse events and assigning the attribution for each event for all subjects enrolled on the trial.

Table 3. 2008 IWCLL Grading for Hematological Toxicity	Decrease in PLT* or HGB** (nadir) from pretreatment value, %	Absolute neutrophil count (ANC)/I*** (nadir)
Grade		
0	10%	2000
1	11 – 24%	1500 – < 2000
2	25 – 49%	1000 – < 1500
3	50 – 74%	500 – < 1000
4	75%	< 500

If any abnormal laboratory result is considered clinically significant, the investigator must provide details about the action taken with respect to the test drug and about the patient's outcome.

### **M.D. Anderson (Sponsor) Reporting Requirements for Serious Adverse Events and Dose Limiting Toxicities:**

As per MDACC and Leukemia phase II-III studies.

#### **Serious Adverse Event (SAE) Definition**

A serious adverse event is one that at any dose (including overdose):

Results in death.

Is life-threatening.

Requires inpatient hospitalization or prolongation of existing hospitalization.

Results in persistent or significant disability or incapacity.

Is a congenital anomaly or birth defect.

Is an important medical event.

#### Suspected Positive Pregnancy

“Life-threatening” means that the subject was at immediate risk of death at the time of the serious adverse event; it does not refer to a serious adverse event that hypothetically might have caused death if it were more severe.

“Persistent or significant disability or incapacity” means that there is a substantial disruption of a person’s ability to carry out normal life functions.

Medical and scientific judgment should be exercised in deciding whether expedited reporting is appropriate in situations where none of the outcomes listed above occurred. Important medical events that may not be immediately life-threatening or result in death or hospitalization but may jeopardize the patient or may require intervention to prevent one of the other outcomes listed in the definition above should also usually be considered serious. Examples of such events include allergic bronchospasm requiring intensive treatment in an emergency room or at home, blood dyscrasias or convulsions that do not result in inpatient hospitalization, or the development of drug dependency or drug abuse. A new diagnosis of cancer during the course of a treatment should be considered as medically important.

**Serious Adverse Events Reporting:** The principal investigator has the obligation to report all serious adverse events to The University of Texas, M. D. Anderson Cancer Center (MDACC) IRB, GSK and NCCN within 24 hours.

Email [contact] or

Fax SAEs to: [name]

AND

Email: [[contact]](mailto:[contact]) or [contact]

All serious adverse events not requiring expedited reporting should be reported to MDACC IRB within 5 business days. All deaths during treatment or within 30 days following completion of active protocol therapy must be reported within 24 hours of knowledge regardless of the attribution. SAEs beyond 4 weeks after the end of study drug administration will be reported if thought to be drug related, in compliance with MDACC IRB, GSK and NCCN required SAE reporting requirements.

#### **Investigator Reporting Responsibilities**

The conduct of the study will comply with all FDA safety reporting requirements. **Serious Adverse Events Reporting:** The principal investigator has the obligation

to report all serious adverse events to MDACC IRB, GSK and NCCN within 24 hours.

### **Annual Reports**

All adverse experience reports must include the patient number, age, sex, severity of reaction (mild, moderate, severe), relationship to study drug (probably related, unknown relationship, definitely not related), date and time of administration of test medications and all concomitant medications, and medical treatment provided. The investigator is responsible for evaluating all adverse events to determine whether criteria for "serious" and as defined above are present. The investigator is responsible for reporting adverse events to MDACC IRB, GSK and NCCN as described below.

### **Expedited reporting by Principal Investigator to GSK**

Serious adverse events (SAE) are defined above. The investigator should inform GSK and NCCN of any SAE within 24 hours of being aware of the event. The date of awareness should be noted on the report. This must be documented on an M. D. Anderson SAE form. This form must be completed and supplied to MDACC IRB, NCCN and GSK within 24 hours/1 business day at the latest on the following working day. The initial report must be as complete as possible, including details of the current illness and (serious) adverse event, and an assessment of the causal relationship between the event and the study drug. Information not available at the time of the initial report (e.g., an end date for the adverse event or laboratory values received after the report) must be documented on a follow-up M. D. Anderson SAE form. A final report to document resolution of the SAE is required. The GSK protocol number (115857) should be included on SAE reports to GSK and NCCN. A copy of the fax transmission confirmation of the SAE report to GSK and NCCN should be attached to the SAE and retained with the patient records.

### **Report of Adverse Events to the Institutional Review Board**

The principal Investigator is required to notify his/her Institutional Review Board (IRB) of a serious adverse event according to institutional policy.

### **Sponsor Reporting to the FDA**

Adverse drug reactions that are Serious, Unlisted/unexpected, and at least possibly associated to the drug, and that have not previously been reported in the Investigators brochure, or reference safety information document should be reported promptly to the Food and Drug Administration (FDA). A clear description of the suspected reaction should be provided along with an assessment as to whether the event is drug or disease related.

The sponsor shall notify the FDA by telephone or by fax of any unexpected fatal or life threatening experience associated with the use of the drug. As soon as possible, but no later than 7 calendar days after the sponsors initial receipt of the information. Each phone call or fax shall be transmitted to the FDA new drug review division in the Center for Drug Evaluation and Research or the product review division in the Center for Biologics Evaluation and Research that has responsibility for review of the IND if applicable.

### **Adverse event updates and safety reports**

- 1.GSK shall notify the Investigator via a Safety Report of the following information:
- 2.Any AE associated with the use of study drug in this study or in other studies that is both serious and unexpected.
- 3.Any finding from tests in laboratory animals that suggests a significant risk for human subjects including reports of mutagenicity, teratogenicity, or carcinogenicity.
- 4.The Investigator shall notify his/her IRB/EC promptly of these new serious and unexpected AE(s) or significant risks to subjects.
- 5.The Investigator must keep copies of all AE information, including correspondence with GSK and the IRB/EC, on file.

### **Protocol amendments**

Any amendment to this protocol must be agreed to by the Principal Investigator and reviewed by NCCN and GSK. Amendments should only be submitted to IRB/EC after consideration of NCCN and GSK review. Written verification of IRB/EC approval will be obtained before any amendment is implemented.

### **Protocol deviations**

When an emergency occurs that requires a deviation from the protocol for a subject, a deviation will be made only for that subject. A decision will be made as soon as possible to determine whether or not the subject (for whom the deviation from protocol was effected) is to continue in the study. The subject's medical records will completely describe the deviation from the protocol and state the reasons for such deviation. In addition, the Investigator will notify the IRB/EC in writing of such deviation from protocol.

### **9.0 Optional Correlative Studies**

#### **Ofatumumab serum levels**

Ofatumumab serum levels will be measured at baseline, 1 week, and month 3, 6, 9 and 12. Samples will be collected and shipped to GSK for analysis as ofatumumab assays are proprietary to GSK and must be used through them.

### **miRNA plasma levels and profiling**

Selected miRNA plasma levels in CLL patients will be determined.

Genome-wide profiling study on plasma samples collected from all the patients before the start of the treatment and we will further perform follow-up studies at specific time points (month 3, 6, 9 and 12) will be conducted by quantitative RT-PCR (Rossi et al., Blood 116, 945-952 2010).

### **10.0 Statistical design**

This is a phase II trial to assess the activity and tolerability of ofatumumab in elderly (age 65 or greater), unfit patients with previously untreated CLL.

Response will be assessed after month 3, month 6 and every 6 months thereafter using the 2008 NCI-WG criteria. Toxicity will be score using CTCAE v4.0. The first time point to evaluate efficacy and toxicity will be at completion of month 6 of treatment. Toxicity will be monitored during the entire treatment.

The primary endpoint of this study is OR (CR + PR) and a Simon's two-stage optimum design will be used for this study. A sample size of 34 is chosen to differentiate between a good response rate of 70% and a poor response rate of 40% with 95% power at a significance level of 0.05. The trial will stop early due to lack of efficacy if there are 6 or fewer patients with OR in the first 14 patients. Lack of efficacy will also occur if there are 18 or fewer responses in 34 patients. Secondary endpoints are progression-free survival (PFS) and CR rate. PFS is defined as time from start of therapy to death or progression of disease and it will be calculated using Kaplan Meier estimates. Responses will be assessed by Fisher's exact test with intention to treatment analysis by pre-treatment characteristics. Potential relationships between ofatumumab plasma concentrations and clinical outcomes (e.g. OR) will be explored using regression analyses.

For the correlative studies, we will assess the association between survival data and miRNA marker expression using proportional hazards models and estimate the distributions of time-to-event outcomes using the Kaplan and Meier method. We will then compare these distributions among treatment or cohort groups using the log-rank test. We will compare the proportions of complete responses between positively and negatively expressed miRNAs that are therapeutic markers in various trials. Fifty-eight samples (2-3 sequential samples from each patient) will be required to achieve 80% power at a 2-sided significance level of 0.05 and Bonferroni adjustment for testing 10 markers, assuming that 50%

patients are marker positive and that the response rates in the positively and negatively expressed markers are 75% and 25%, respectively.

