### **Rationale for Use of Ofatumumab in CLL**

The rationale for evaluating the activity of ofatumumab in elderly patients with CLL is based on the experience with rituximab. Two clinical studies have been conducted at our center evaluating the activity of monotherapy with rituximab as initial treatment of patients with CLL. One study focused on the activity of rituximab in patients without indications for treatment, but with high-risk for progression based on beta2 microglobulin level. In this subset of patients the overall response (OR) rate was 82% and the duration of response was 23 months ([name] et al., Cancer 2011). In a subsequent study, we treated 32 patients age 70 or older with rituximab in association with GM-CSF. All patients had indication for treatment and patients with poor performance status were allowed to participate. In this group the OR rate was 69% and the median duration of response was 18 months ([name], et al. Leuk and Lymph, 2009). This elderly group tolerated the treatment well, with toxicity limited to infusion reactions.

Ofatumumab therefore, with its favorable toxicity profile, its clinical activity in the relapsed/refractory setting, and in vitro studies suggest that ofatumumab has greater complement-dependent cytotoxicity and antibody-dependent cellular cytotoxicity compared to rituximab, is an attractive therapeutic option for elderly patients with CLL requiring initial therapy.

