## **2.0 Objectives**

### **Primary Objective:**

1.1 To evaluate the overall response rate of ofatumumab in the upfront setting in elderly, unfit patients with CLL. [Unfit patients in this trial are: patients with an ECOG/WHO performance status of 2-3 (usually defined as "slow-go or no-go") or patients with an ECOG/WHO performance status of 0-1 and a CIRS or Charlson (Charlson, 1987 J Chronic Dis 40(5): 373-83) co-morbidity score of 2 or higher.]

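### Does the lack of a stated assessment window for overall response undermine the two-stage design?

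*Combined protocol and SAP*

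**What the plan says.** Section 10.0 states "The primary endpoint of this study is OR (CR + PR"), and the primary objective in Section 2.0 is "To evaluate the overall response rate of ofatumumab in the upfront setting in elderly, unfit patients with CLL". Neither gives a time. Section 7.0 sets the schedule: "Response will be assessed after month 3, month 6 and every 6 months thereafter". Section 10.0 repeats it with the 2008 NCI Working Group criteria and then adds "The first time point to evaluate efficacy and toxicity will be at completion of month 6 of treatment".

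The two decision rules follow in the same paragraph: "The trial will stop early due to lack of efficacy if there are 6 or fewer patients with OR in the first 14 patients" and "Lack of efficacy will also occur if there are 18 or fewer responses in 34 patients". The design is a Simon two-stage optimum with 34 patients, a poor rate of 40%, a good rate of 70%, 95% power and a significance level of 0.05. The two rates come in the sentence directly after the one that names OR as the endpoint. Under the Treatment Plan in Section 3.0, dosing runs to month 12, so month 6 falls during treatment.

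**The concern.** Calling month 6 the first evaluation fixes the earliest look. It does not say when a response stops counting, and the assessment schedule has no stated end. The wording could therefore fit response present at month 6, best response up to month 6, or best response up to month 12 or later. Neither rule names a visit, and the 40% and 70% rates carry no time point or source.

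The planned error rates hold only if responses are counted under the definition to which 40% and 70% refer. If the count is narrower than the good rate assumes, power falls. If it is wider than the poor rate assumes, an inactive treatment passes more often. A patient who responds at month 3 and has lost the response by month 6, or who first responds at month 12, could move the total from 18 (lack of efficacy) to 19. In an open-label single-arm trial there is the further worry that the definition could be settled after the responses are known.

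**Working it through.** **Inputs, all from Section 10.0.** Stage 1 has 14 patients, and the trial stops at 6 or fewer responses. The total is 34 patients, so stage 2 has 34 − 14 = 20, and 18 or fewer responses is lack of efficacy. The poor rate is 0.40 and the good rate 0.70.

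**Step 1: reproduce the plan's design under one OR definition.** Activity is declared if X1 ≥ 7 and X1 + X2 ≥ 19, with X1 ~ Bin(14, p) and X2 ~ Bin(20, p):

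P(declare activity | p) = Σ over x = 7 to 14 of P(X1 = x) × P(X2 ≥ 19 − x).

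| x | P(X1 = x), p = 0.40 | P(X2 ≥ 19 − x), p = 0.40 | Product | P(X1 = x), p = 0.70 | P(X2 ≥ 19 − x), p = 0.70 | Product |
|---|---|---|---|---|---|---|
| 7 | 0.1574 | 0.0565 | 0.0089 | 0.0618 | 0.8867 | 0.0548 |
| 8 | 0.0918 | 0.1275 | 0.0117 | 0.1262 | 0.9520 | 0.1202 |
| 9 | 0.0408 | 0.2447 | 0.0100 | 0.1963 | 0.9829 | 0.1930 |
| 10 | 0.0136 | 0.4044 | 0.0055 | 0.2290 | 0.9949 | 0.2279 |
| 11 to 14 | | | 0.0024 | | | 0.3549 |
| **Sum** | | | **0.0385** | | | **0.9507** |

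The type I error is within 0.05 and the power meets 95%. The chance of stopping at stage 1, P(X1 ≤ 6), is 0.692 at 40% and 0.031 at 70%. The expected sample size at 40% is 14 + 20 × (1 − 0.692) = 20.15, using the unrounded probability. A search over all two-stage designs with up to 41 patients, type I error at most 0.05 and power at least 0.95 returns this same design as the one with the smallest expected size at 40%. The sample size and both cut-offs are what the method gives.

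**Step 2: does the choice of month change these figures?** The formula uses only p. Any single definition, whether month 6, best by month 6 or best by month 12, gives 0.0385 and 0.9507 as long as 40% and 70% are the poor and good rates under it. The window matters only if the rates were set for one definition and the count uses another.

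**Step 3: how much would a mismatch cost?** The documents give no month-6 rate against a later rate, so these inputs are assumptions. The same formula at both stages gives:

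| True rate under the definition counted | P(declare activity) |
|---|---|
| 70% (as planned) | 0.951 |
| 65% | 0.861 |
| 60% | 0.699 |
| 45% (if 40% was meant for a narrower definition) | 0.119 |
| 40% (as planned) | 0.0385 |

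A gap of 5 percentage points would matter. These rows show how sensitive the design is to the true rate. They do not show that any gap exists.

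**Step 4: can the documents supply the size of a gap?** The Background gives two response durations. One is for patients aged 70 or older on rituximab with GM-CSF: "In this group the OR rate was 69% and the median duration of response was 18 months". The other is for patients given early rituximab without an indication for treatment: "the overall response (OR) rate was 82% and the duration of response was 23 months". Turning these into a loss between months 3 and 6 needs an assumed hazard shape and a transfer from rituximab regimens to a drug still being dosed at month 6. With a constant hazard, the 18-month figure gives a loss of 1 − 2^(−3/18) = 0.109. If every responder had responded by month 3, the counted rate would be 0.70 × (1 − 0.109) = 0.624 and power 0.784. With a rising hazard (Weibull, shape 1.5) the loss is 0.046, and power is about 0.90 under the same assumption. The answer depends on the curve chosen, so it cannot be called a property of this plan.

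**The case for a change.** The strongest case for acting is that a primary endpoint should be fixed in writing before responses are seen, above all when the trial is open-label and the verdict turns on one count. Power exceeds its target by only 0.0007, so almost any narrowing of the counted rate takes it below 95%. One sentence would close the gap.

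Part of this stands. No section gives a closing month or a best-response rule, and month 6 is only an earliest look. A clarifying sentence would be tidy.

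The rest does not carry. Section 10.0 gives 70% and 40% immediately after naming OR as the endpoint, so the natural reading is that they are rates of that endpoint. Month 6 is placed just before the stopping rules, so stage 1 is not untimed. Part of the definition is delegated to the 2008 criteria, which are not reproduced in the documents, so the list of admissible definitions cannot be settled from the documents alone. Removal from study for lack of therapeutic effect (Section 5.0) may also make late responses rarer. Finally, the choice between month 6 and month 12 is a trade-off: the first gives an earlier stage 1 decision, while the second counts later responders and delays that decision by 6 months. Neither is the correct answer that the plan missed.

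**Conclusion.** The concern identifies missing detail, and no error is shown. Under one OR definition for both rules, with 40% and 70% as rates of that endpoint, the plan's design reproduces exactly (type I error 0.0385, power 0.9507), and 34 patients with cut-offs of 6/14 and 18/34 need no revision. Every less favourable figure rests on a response rate, hazard shape or late-response rate that the documents do not give for this treatment. The power of 0.861 at 65% and 0.699 at 60% shows sensitivity to an assumed mismatch and is not evidence of one.

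The analysts can fill the gap sensibly by using one definition at both stages, no earlier than month 6, recorded before the 14-patient count is made and reported with the result. This conclusion assumes that reading. It would need another look only if the sponsor said that 40% and 70% were set for a different definition from the one counted.

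### Response by pre-treatment characteristics is to be tested only with Fisher's exact test, so continuous baseline measures must be grouped at unstated cut-offs, at some cost in power to an exploratory analysis

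*Combined protocol and SAP*

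**What the plan says.** Section 10.0 (Statistical design) gives one sentence to the relation between response and baseline features: "Responses will be assessed by Fisher's exact test with intention to treatment analysis by pre-treatment characteristics". It lists no characteristics, cut-offs, effect size, power or multiplicity rule for that analysis.

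The other models in the section serve other questions. Regression is tied to drug exposure: "Potential relationships between ofatumumab plasma concentrations and clinical outcomes (e.g. OR) will be explored using regression analyses". Proportional hazards models are tied to miRNA markers and survival.

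Section 6.0 (Pretreatment evaluation) collects several measures on a continuous scale, including "Beta-2-microglobulin (within 7 days of registration") and "Complete CBC and differential and peripheral blood lymphocyte subset and immunoglobulin levels (within 7 days of registration"). It also collects creatinine. Section 4.0 adds age, eGFR and a CIRS or Charlson score. Some characteristics are naturally categorical: IgVH mutation status, cytogenetic abnormalities and the performance-status groups in the entry criteria.

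**The concern.** Fisher's exact test works on a contingency table. A continuous or ordinal measure can enter it only after being cut into groups. This raises three issues:

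- Cutting discards information, and only 34 patients are planned.
- Fisher's test on a small table is conservative, which costs further power.
- With no cut-off fixed beforehand, the reported result can depend on where someone later places the cut.

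At stake is the plan's only analysis of which elderly, unfit patients respond according to clinical baseline features. Beta-2-microglobulin is a natural candidate: the rationale in Section 1.0 cites a rituximab study in patients at "high-risk for progression based on beta2 microglobulin level".

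**Working it through.** **1. The plan's own design.** Section 10.0 states: "A sample size of 34 is chosen to differentiate between a good response rate of 70% and a poor response rate of 40"%. The type I error is set at 0.05 and the power at 95%. The stage 1 rule is: "The trial will stop early due to lack of efficacy if there are 6 or fewer patients with OR in the first 14 patients". The final rule is failure at 18 or fewer responses in 34. The probability of declaring activity is the sum over x = 7 to 14 of P(X1 = x) × P(X2 ≥ 19 − x), with X1 ~ Bin(14, p) and X2 ~ Bin(20, p). This gives 0.0385 at p = 0.40 and 0.9507 at p = 0.70, so the primary design reproduces. It does not use the baseline comparison. The documents state no power for that comparison, so there is no figure to reproduce.

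**2. Actual size of Fisher's test.** A median cut of 34 patients gives 17 and 17. The size is the sum, over all (a, b) with a two-sided Fisher p-value of 0.05 or less, of Bin(a; 17, p) × Bin(b; 17, p). It is 0.022 at p = 0.40, 0.024 at p = 0.50 and 0.020 at p = 0.70, so about 2% against a nominal 5%.

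**3. Power under a graded relation.** The assumptions below are mine, because the documents give none:

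- 34 patients and a two-sided 0.05 level.
- Baseline value x ~ N(0, 1).
- Response occurs if ρx + √(1 − ρ²)e exceeds a threshold, with e ~ N(0, 1) and the threshold set to give the overall response rate.
- Fisher's test and an uncorrected chi-square test use the same median split. The rank-sum test uses uncut x.

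Results from 10,000 simulated trials per row, in %; the gaps are in percentage points and were computed before rounding:

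| Response rate | ρ | Fisher | Chi-square | Rank-sum | Rank-sum minus Fisher | Of which cutting (rank-sum minus chi-square) |
|---|---|---|---|---|---|---|
| 40% | 0.2 | 6 | 12 | 13 | 7 | 2 |
| 40% | 0.3 | 12 | 20 | 26 | 14 | 5 |
| 40% | 0.4 | 20 | 32 | 43 | 22 | 10 |
| 40% | 0.6 | 52 | 66 | 82 | 30 | 16 |
| 55% | 0.2 | 7 | 13 | 14 | 8 | 2 |
| 55% | 0.3 | 12 | 21 | 26 | 14 | 5 |
| 55% | 0.4 | 22 | 35 | 43 | 21 | 8 |
| 55% | 0.6 | 54 | 68 | 82 | 28 | 14 |
| 70% | 0.2 | 5 | 10 | 13 | 8 | 3 |
| 70% | 0.3 | 10 | 17 | 24 | 14 | 7 |
| 70% | 0.4 | 17 | 28 | 39 | 22 | 11 |
| 70% | 0.6 | 46 | 61 | 78 | 32 | 18 |

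Cutting accounts for about 40-56% of the loss at ρ = 0.4-0.6 and for less at ρ = 0.2-0.3. The rest is Fisher's conservatism. With no association (ρ = 0), Fisher's test rejects in about 2% of trials and the rank-sum test in 4-5%.

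**4. A second model.** With a logistic relation and odds ratios of 2 to 5 per SD, the loss against the rank-sum test is about 20-32 points. At 1.5 per SD it is about 8-10 points, and at 8 per SD about 12-20. The only between-group contrast in Section 10.0 is 75% against 25%, stated for miRNA markers. Halves with those response rates correspond to an odds ratio of about 5.3 per SD, and power is then 76% for Fisher's test against 95% for the rank-sum test.

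**5. Sensitivity to the cut.** At ρ = 0.5 and 55% response, I cut each simulated trial near the lower tertile, at the median and near the upper tertile. The three Fisher verdicts disagreed in 43% of trials.

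**6. The case that favours grouping.** If response is a step exactly at the median cut, Fisher against rank-sum is 79% against 74% for 75% vs 25%, 31% against 32% for 70% vs 40%, and 34% against 37% for 85% vs 55%.

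**The case against.** The strongest reply is that no objective depends on this analysis. Section 2.0 does not list baseline predictors of response, and the go/no-go decision rests on 6/14 and 18/34. Section 10.0 does not say which characteristics are meant, and Fisher's test is right for the categorical ones. The remark on beta-2-microglobulin in Section 1.0 describes an earlier study, not an analysis planned here. All of this stands, and it is why the point is minor. It does not supply a method for the continuous measures.

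A reader might infer that the plan simply loses 20-32 points of power. The documents do not support that as an unconditional figure. It needs a moderate-to-strong graded effect, a cut near the median and all 34 patients enrolled, none of which is given for this analysis. Nor should the whole loss be put down to cutting.

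A reader might also infer that real predictors would be reported as showing no association. That goes too far. At ρ = 0.6 and 55% response Fisher's test still detects 54%, and at ρ = 0.4 the rank-sum test itself misses 57-61%. With 34 patients, and about 10 non-responders at a 70% response rate (0.3 × 34), modest effects are hard to detect by either method.

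Finally, moving from a size of about 2% to about 5% admits more false positives. For six unassociated characteristics the expected number rises from about 6 × 0.02 = 0.12 to 6 × 0.05 = 0.30. This stands and has to be stated with the fix.

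**Conclusion.** The point holds as a minor one. Fisher's exact test is the only method named for response by pre-treatment characteristics, so continuous and ordinal measures can be tested only after grouping at cut-offs that the plan does not state. Assuming 34 patients, a graded relation and a median cut, the power given up against a rank-sum test is about 7-14 points for latent correlations of 0.2-0.3 and about 20-32 points for 0.4-0.6. At the larger effects about half of this is due to cutting and the rest to the test's actual size of about 2%. The analysis is exploratory, and the two-stage decision on overall response is untouched.

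**What to change.** In Section 10.0, replace the sentence with wording to this effect:

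- Categorical pre-treatment characteristics are compared by Fisher's exact test.
- Continuous or ordinal characteristics (for example age, beta-2-microglobulin, blood counts, immunoglobulin levels, eGFR, co-morbidity score) are analysed on their measured scale. The Wilcoxon rank-sum test is the single test, and an odds ratio with 95% CI from a one-covariate logistic model is given for description only.
- Grouped response tables are descriptive.
- All of this is by intention to treat, exploratory and unadjusted for multiplicity.

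The cost is a few lines of text, with no new data, visits or patients. There are two small downsides. If the true effect is a step exactly at the cut that would have been used, Fisher's test may do slightly better (about 4-5 points at 75% vs 25%, no advantage in the two smaller contrasts checked). The false-positive rate per test also rises from about 2% to the nominal 5%.
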